### **6.2.1.3 Reporting**

Subjects will be queried regarding AEs at all in-clinic visits and at follow-up phone calls during the single-blind placebo run-in phase and the double-blind phase. The investigator will assess and record all reported AEs. Any AE newly reported after receiving the last dose of study medication will be followed up until 30 days.

A death occurring during the study, or which comes to the attention of the investigator within 30 days after stopping the treatment whether considered treatment-related or not, must be reported to the sponsor.

For all SAEs, including an abnormal laboratory test value, the investigator must inform the Medical Monitor (MM) by telephone no later than 24 hours after becoming aware of the event. Subsequently, the SAE must be assessed for the following details: seriousness of event, start date, stop date, intensity, frequency, relationship to study drug, action taken regarding study drug, treatment required, outcome to date, and other data as indicated on the SAE form. All details regarding the SAE must be recorded on the SAE form that is provided. The SAE reporting contact information is as follows:

Medical Monitor [name] (direct) or [name] (mobile) and email [[contact]](mailto:[contact]). Such preliminary reports will be followed by detailed descriptions later, which may include copies of hospital case reports, autopsy reports, and other related documents when requested.

The IRB will be notified of such an event in writing as soon as is practical in compliance with federal and local regulations.

### **6.2.1.4 Suspected Technical Device Issues**

If a device is suspected of having technical issues (e.g., damaged device, missing parts, inoperable device), the nature of the technical issue should be reviewed by the investigator to determine if the issue resulted in an AE or SAE and that this event is documented and reported appropriately.

If the investigator suspects that a technical device issue does exist, then the issue must be

---

reported by the investigational staff within 1 working day of their knowledge of the event using the Technical Device Issue Notification Form.

## **Unanticipated Adverse Device Effects**

The definition of unanticipated adverse device effects (UADEs), which are device effects that are reportable on an expedited basis in the United States is as follows:

An UADE is defined as a serious adverse effect on health or safety or any life-threatening problem or death caused by, or associated with, a device, if that effect, problem, or death was not previously identified in nature, severity, or degree of incidence in the investigational plan or application (including a supplementary plan or application), or any other unanticipated serious problem associated with a device that relates to the right, safety, or welfare of subjects.

For investigational devices, sponsors are required to collect, track, and review all potential UADEs.

- 1) Site collects all AEs on CRF form
- 2) AEs that are deemed to be related to the investigational device are called adverse device effects (ADEs). ADEs require further review, typically done by the MM.
- 3) The site would complete an ADE form (similar to an SAE form), submit to the contract research organization (CRO)/sponsor. Medical Monitor would review and determine if the ADE complies with the definition of a UADE.
- 4) If the effect is indeed a UADE, the UADE is then reported to the FDA within 10 days of notification to sponsor. Reporting time is 5 days if remedial action is needed, such as changes to instructions for use of device, subject population or stopping clinical trial altogether.
- 5) Anything reported to FDA must also be reported to IRBs.

### **6.2.2 Physical and Neurological Examination**

Physical and neurological examination will be performed at Visits 1 and 3, and will include assessments of head, eyes, ears, nose, throat, lymph nodes, skin, extremities, respiratory, gastrointestinal, musculoskeletal, cardiovascular, and nervous systems. A nasal examination using a speculum will be conducted at Visits 1, 2, and 3 to ensure that the subject does not have nasal obstruction due to nasal septum deviation, polyposis, severe mucosal swelling, or any other reason. The physical/neurological and nasal examinations should be performed by the same person each time, whenever possible.

---

Physical examination abnormalities determined by the investigator to be clinically significant at screening/enrollment should be recorded as medical history. Any clinically significant changes in physical examination findings from the screening examination should be recorded as AEs.

### **6.2.3        Vital Signs**

Vital signs, systolic and diastolic blood pressure (mm Hg), heart rate (beats/minute), respiratory rate (breaths/minute) and body temperature (°F) should be recorded at Visit 1.

Weight and height should be measured at Visit 1.

### **6.2.4        Urine Drug Screen Tests**

Urine samples will be analyzed at the study site at all clinic visits (Visit 1 to 3) for the following: marijuana, opiates, amphetamines, cocaine, phencyclidine, barbiturates, benzodiazepines and methadone.

### **6.2.5        Pregnancy Tests**

Urine pregnancy tests are to be performed for females of childbearing potential at all clinic visits (Visit 1 to 3).

All female subjects of childbearing potential should be instructed to use appropriate birth control methods for up to 4 weeks following the last dose of study medication.

### **6.2.6        Columbia Suicide Severity Rating Scale (C-SSRS)**

The C-SSRS (Appendix 3) is a low-burden measure of the spectrum of suicidal ideation and behavior that was developed by Columbia University researchers for the National Institute of Mental Health Treatment of Adolescent Suicide Attempters Study to assess severity and track suicidal events through any treatment. It is a clinical interview providing a summary of both ideation and behavior that can be administered during any evaluation or risk assessment to identify the level and type of suicidality present. The C-SSRS can also be used during treatment to monitor for clinical worsening.

The C-SSRS evaluation will be performed at all clinic visits (Visit 1 ['baseline/screening' version], Visit 2 and Visit 3 ['since last visit' version]).

## **6.3            Schedule of Evaluations and Procedures**

A schedule of evaluations and procedures by study visit is provided in [Table 1](#). The schedule for

---

evaluations and their frequency during a migraine attack is provided in [Table 2](#).

### **6.3.1 Description of Study Procedures**

#### **6.3.1.1 Visit 1 (Screening/Enrollment)**

The following procedures should be performed at screening/enrollment (Day -3 to 1)

1. The investigator will provide the subject and their parent/legal guardian with assent /ICF and privacy documents for signature and will explain the rationale for the study, providing ample time for participants, and/or authorized representatives to ask questions
2. Review and record medical and migraine history
3. Review and record prior and concomitant medications
4. Query subject on any adverse events
5. Review eligibility (inclusion/exclusion criteria)
6. Perform physical and neurological examination including nasal examination
7. Measure and record vital signs, height and weight
8. Collect urine specimen for drug screen
9. Urine pregnancy test (for females of childbearing potential only)
10. Administer the C-SSRS
11. Train subject on the use of study medication
12. Access IWRS to obtain assigned kit number for study medication
13. Dispense diary and study medication

Subjects will be instructed to treat one migraine headache of moderate to severe intensity in the subsequent 12 weeks (84 days) with the study medication and to respond to questions on the study diary. Diary should be used before taking the study treatment and at 15, 30, 60, 120 min, 3 hours, 4 hours, and 24 hours after dosing. A monthly phone call to the subject or their parent/legal guardian will be placed by site personnel to inquire about any adverse events and to answer study question.

Following treatment in the single-blind placebo run-in phase, the site will complete a protocol eligibility form and submit to the MM for approval. Subjects deemed eligible by the investigator and the MM will be enrolled into the study.

---

### **6.3.1.2 Visit 2 (Randomization)**

The following procedures should be performed at Visit 2

1. Review and record medical and migraine history
2. Review and record prior and concomitant medications
3. Review eligibility (inclusion/exclusion criteria)
4. Collect urine specimen for drug screen
5. Urine pregnancy test (for females of childbearing potential only)
6. Administer the C-SSRS
7. Train subject on the use of study medication
8. Query subject on any adverse events
9. Perform nasal examination
10. Review diary and return to subject
11. Randomization
12. Access IWRs to obtain assigned kit number for study medication
13. Dispense study medication

Subjects will be instructed to treat one migraine headache of moderate to severe intensity in the subsequent 12 weeks (84 days) with the study medication and to respond to questions on the study diary. Diary should be used before taking the study treatment and at 15, 30, 60, 120 min, 3 hours, 4 hours, and 24 hours after dosing. A monthly phone call to the subject or their parent/legal guardian will be placed by site personnel to inquire about any adverse events or to answer study question.

### **6.3.1.3 Visit 3 (Exit/Early Termination)**

The following procedures should be performed at Visit 3.

1. Review and record concomitant medications
2. Perform physical and neurological examination including nasal examination
3. Query subject on any adverse events
4. Collect urine specimen for drug screen
5. Urine pregnancy test (for females of childbearing potential only)

6. Administer the C-SSRS
7. Collect diary and study medication
8. Access IWRS to record subject exit

#### **6.3.1.4 Follow-up Phone Visits**

The investigator will follow-up with monthly telephone calls after the screening/enrollment visit and after the randomization visit for up to 12 weeks depending on when a migraine attack is treated. During these phone visits, subjects will be queried on adverse events and any concomitant medications taken.

#### **6.3.1.5 Procedures During Treatment**

Subjects will be instructed to administer their study medication at the onset of a migraine attack and enter the information in the diary. The schedule of procedures is outlined in [Table 2](#).

## 7           **DATA MANAGEMENT**

### **7.1           Data Collection**

The sponsor or designated representative (e.g., CRO) will perform the data management activities in accordance with the data management plan (DMP). The DMP will outline the systems and procedures to be used in the study.

Clinical study data will be reported (captured) by study site personnel on eCRFs. An eCRF must be completed for every subject enrolled in the study. The eCRF data will be entered by trained study-site personnel and then reviewed for completeness and accuracy and electronically signed by the investigator or authorized designee. All study-site personnel must use a password-protected user account to enter, review, or correct study data. Electronic signature procedures shall comply with the CFR Title 21 Part 11. Passwords will be strictly confidential.

All eCRF data will be exported from the electronic data capture (EDC) system and transferred to the sponsor or representative. The sponsor or representative will also receive electronic transfers of non-eCRF data from third-party vendors as appropriate. The electronic data format of all transfers will be agreed upon with the sponsor or representative and documented in the DMP or vendor data transfer requirements document as appropriate. The clinical monitoring staff will perform source data verification (SDV) of the data recorded in the EDC system with source documents at the clinical study sites according to the data management plan and clinical monitoring plan. The data will be subjected to consistency and validation checks within the EDC system with supplemental data reviews performed outside of the EDC system.

Medical history and adverse events will be coded using a current version of Medical Dictionary for Regulatory Activities (MedDRA), and concomitant medications using a current version of the World Health Organization (WHO) Drug Dictionary. The sponsor or representative will perform a medical safety review of the coding.

Completed eCRF images with a date- and time-stamped electronic audit trail indicating the user, the data entered, and any reason for change (if applicable) will be archived at the investigator's site and at the sponsor's site.

## 8 STATISTICAL METHODS

### 8.1 Analysis Populations

Two analysis populations will be used; modified intent-to-treat (mITT) and safety. The mITT population includes all subjects randomized and treated for Migraine Attack 2 who have at least one post-baseline efficacy assessment and will be used for all analyses of efficacy. Subjects in the mITT population will be included in the treatment group to which they were randomized regardless of treatment received. The safety population includes all subjects who received study treatment and will be used for all analyses of safety. Subjects will be included in the treatment group based on the actual treatment received.

### 8.2 Efficacy Analysis

The primary efficacy endpoint of the study is headache pain-free at 120 minutes following treatment of Migraine Attack 2. Treatment comparison will be performed by using the Cochran-Mantel-Haenszel (CMH) test stratified by age group (12-14 years or 15-17 years) and baseline migraine pain severity (moderate or severe). Secondary and exploratory efficacy endpoints will be analyzed similarly, or appropriate statistical tests will be used. Efficacy assessments after taking rescue medication will be set to missing. Missing data will be imputed by treatment failure, i.e., headache pain-free = no. *Secondary efficacy endpoints (Migraine Attack 2):*

- Headache relief (defined as a reduction in pain intensity from moderate or severe [grade 2 or 3] at baseline to none or mild [grade 0 or 1] at 120 minutes)
- Headache pain-free by time (other than at 120 minutes)
- Headache relief by time (other than at 120 minutes)
- Change from baseline in headache severity by time
- Sustained pain relief, defined as headache relief [headache severity mild (grade 1) or none (grade 0)] at 2 hours with no worsening of headache, use of a second dose of study medication, or rescue medication taken through 24 hours after dose
- Sustained pain freedom, defined as pain freedom [headache severity none (grade 0)] at 2 hours with no recurrence of headache, use of a second dose of study medication or rescue medication taken through 24 hours after dose
- Rescue medication use and time to rescue medication
- Number of subjects with nausea, phonophobia, photophobia, or vomiting by time
- Number of subjects who return to ‘normal’ functioning by time

---

- Time to recurrence of headache defined as an increase from a headache severity score of 0 (none) or 1 (mild) at 2 hours to 2 (moderate) or 3 (severe) within 24 hours

*Exploratory efficacy endpoints (Migraine Attack 2):*

- Sustained pain relief (1 to 2 hours), defined as headache relief [Headache severity mild (grade 1) or none (grade 0)] at 60 minutes with no worsening of headache, use of a second dose of study medication, or rescue medication taken through 120 minutes after dose
- Sustained pain freedom (1 to 2 hours), defined as pain freedom [Headache severity none (grade 0)] at 60 minutes with no recurrence of headache, use of a second dose of study medication or rescue medication taken through 120 minutes after dose
- Bilateral headache at predefined timepoints
- Headache intensity increased by movement at predefined timepoints

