There are 2 non-blinded, single-dose, single-center studies that examine the pharmacokinetics of intranasal sumatriptan in children aged 6 to 11 years (Study SUM40254) and in adolescents aged 12 to 17 years (Study SUMB1006). Both studies were conducted in patients diagnosed with migraine and demonstrated that pharmacokinetic parameters outside of a migraine attack in adolescents are similar to those previously reported in adults, suggesting that adolescents should be dosed similarly to adults. Given the dose adjustment scheme used in these studies based on age and bodyweight, there were no clinically significant differences in sumatriptan exposure between adults, adolescents, and children. Various doses and formulations of sumatriptan have been widely studied in adolescents, including subcutaneous, oral, and nasal spray formulations. Of the studies designed as placebo-controlled trials evaluating pain relief following treatment of a moderate-to-severe migraine attack, all failed to demonstrate efficacy for the primary endpoints, primarily due to high placebo response. For this reason, sumatriptan has not yet been approved by the FDA for use in adolescents with migraine. However, efficacy was demonstrated through secondary endpoints and pooled analysis suggesting a high probability of achieving pain freedom at 2 hours following treatment with 20 mg sumatriptan nasal spray. Based on these results, the 2004 American Academy of Neurology (AAN) Practice parameter on the pharmacologic treatment of migraine headache in children and adolescents concluded that sumatriptan nasal spray is effective and should be considered for the acute treatment of migraine in adolescents.

ONZETRA® Xsail® (AVP-825) is a novel intranasal delivery system containing low-dose sumatriptan powder, approved for the acute treatment of migraine with and without aura in adults (ONZETRA Xsail Prescribing Information, 2016). AVP-825 uses a Breath Powered® intranasal delivery system that widens nasal passages and naturally seals the soft palate, while using the patients' exhaled air to propel sumatriptan-powder into the nostril and deliver drug

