### 3 STUDY DESIGN

This is a Phase 3, multicenter, randomized, double-blind, placebo-controlled study evaluating AVP-825 for the acute treatment of migraine with or without aura in adolescent subjects (12 to 17 years old). This study includes 2 treatment phases; a single-blind placebo run-in phase and a double-blind placebo-controlled treatment phase. A schematic of the study design is presented in [Figure 1](#).

Approximately 420 subjects will be enrolled in the single-blind placebo run in phase to obtain approximately 236 subjects randomized in the double-blind treatment phase. Subjects will be enrolled in the study for up to approximately 28 weeks; with up to 12-weeks in a single-blind placebo run-in period, and up to 12-weeks in a double-blind treatment period. An exit/early termination visit will occur 10 days after treatment of Migraine Attack 2. The investigational product in this study is ONZETRA Xsail 22 mg (AVP-825, sumatriptan nasal powder 11 mg per nosepiece) and the control treatment is the same device as AVP-825 with matching placebo nosepieces filled with lactose (i.e. contain no active drug).

All eligible subjects will treat one migraine attack of moderate to severe intensity during the single-blind phase (Migraine Attack 1). Placebo non-responders (defined as subjects who are not headache pain free 2 hours after treatment of Migraine Attack 1) who meet all inclusion/exclusion criteria will be randomized in a 1:1 ratio (active: placebo) to treat one migraine attack of moderate to severe intensity in the double-blind treatment phase (Migraine Attack 2). Randomization will be stratified by age (12 to 14 years versus 15 to 17 years). Enrollment will be monitored to ensure that number of subjects in either age group does not exceed 70% or drop below 30%. Study medication will be administered as soon as possible after the development of a migraine attack associated with moderate-to-severe headache pain during each phase, per the instructions for use (IFU) provided to the subject, and relevant data will be collected in a subject diary.

There are up to 3 scheduled clinic visits including: screening/enrollment (Visit 1), randomization (Visit 2), and exit/early termination (Visit 3). Monthly follow-up phone calls will be made after Visits 1 and 2 for up to 12 weeks after the visit, depending on when Migraine Attacks 1 and 2 are treated.

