**6.1.2 Secondary Measures**

Subjects will record the following in the diary for each migraine attack (1 and 2) at the timepoints specified in Table 2:

- Headache severity score (scale of 0 to 3, where 0 = none, 1 = mild, 2 = moderate, 3 = severe)
- Nausea, vomiting photophobia, phonophobia (yes/no for each symptom)
- Ability to function (response to 'how do you rate your ability to do school-work or perform your usual activities?' on a 5-point scale [normal, mildly impaired, moderately impaired, severely impaired, I require bedrest])
- Time of recurrence of headache, defined as an increase from a headache severity score of 0 (none) or 1 (mild) pain to 2 (moderate) or 3 (severe)
- Use and time of rescue medication
- Bilateral headache (yes/no)
- Intensity increased by movement (yes/no)

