## **8.4 Sample Size Calculations**

Power calculations are based on the results of the completed pivotal trial for adults (OPN-SUM-MIG-3301, Avanir data on file). The observed percentage (n) of subjects experiencing migraine headache pain free at 120 minutes was 34.3% (37) vs. 17.3% (18) for AVP-825 vs. placebo, respectively. For this study in adolescents with single-blind placebo run-in, if it is assumed that the percentage of subjects who are migraine headache pain free at 120 minutes is 30% vs. 15%, a sample size of 236 (118/arm) randomized and treated at Migraine Attack 2 would provide approximately 80% power with 2-sided  $\alpha = 0.05$ . In consideration of the attrition rate during the run-in phase, it is estimated that 420 subjects would be needed to enter the single-blind placebo run-in phase in order to have approximately 236 subjects randomized and treated for Migraine Attack 2.

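### The primary CMH test is valid and reaches its stated power, but it leaves out the Attack 1 two-hour pain grade, a pre-randomization covariate that could add up to about 4 points of power at little cost

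*Combined protocol and SAP*

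**What the plan says.** Section 8.2, and the efficacy paragraph of the synopsis, compare pain freedom at 120 minutes after Attack 2 by a CMH test "stratified by age group (12-14 years or 15-17 years) and baseline migraine pain severity (moderate or severe"). That gives 2 x 2 = 4 strata. Section 3 uses age alone at allocation: "Randomization will be stratified by age (12 to 14 years versus 15 to 17 years"). Attack 1 is not mentioned in the efficacy analysis.

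Attack 1 data are nevertheless collected. Section 6.1.2 opens its list of diary items, which includes the 0 to 3 severity score, with "Subjects will record the following in the diary for each migraine attack (1 and 2) at the timepoints specified in Table 2". Section 3 randomizes only "Placebo non-responders (defined as subjects who are not headache pain free 2 hours after treatment of Migraine Attack 1"). A footnote to Table 2 has the severity score asked whenever the subject is not pain free. In the Visit 2 list (6.3.1.2) the diary review is item 10 and randomization is item 11.

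Section 8.4 states that "a sample size of 236 (118/arm) randomized and treated at Migraine Attack 2 would provide approximately 80% power with 2-sided" alpha of 0.05, for pain-free rates of 30% and 15%.

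**The concern.** The run-in makes sense only if a subject's response to placebo at Attack 1 says something about the response at Attack 2. The plan uses the yes/no part of that information for eligibility and drops the rest. A subject with mild pain two hours after placebo and one still in severe pain enter the primary test as the same risk, given age group and pre-dose severity.

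The grade is fixed before randomization, so adjusting for it does not bias the treatment comparison. If it is prognostic, adjustment adds power without more patients. The sample size carries no margin above 80%, and Section 1 reports that the earlier placebo-controlled adolescent trials of sumatriptan for pain relief "all failed to demonstrate efficacy for the primary endpoints, primarily due to high placebo response". Even a few points of power would be worth having.

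**Working it through.** **1. The plan's own figure.** Inputs from 8.4: 30% vs 15%, two-sided 0.05, 118 per arm.

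- Variance term: 0.30 x 0.70 + 0.15 x 0.85 = 0.3375.
- n per arm = (1.960 + 0.842)^2 x 0.3375 / 0.15^2 = 117.7, so 118.
- Power at 118: 0.15 / sqrt(0.3375/118) = 2.805; 2.805 - 1.960 = 0.845; power 80.1%. With a pooled variance it is 79.2%.

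The stated 236 and about 80% reproduce.

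**2. What adjustment could gain, by formula.** The documents give neither the distribution of the grade nor its prognostic strength, so both are assumed. Take mild/moderate/severe as 35/40/25%, a common odds ratio (OR) per grade, and marginal rates held at 15% and 30%.

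At OR 2 the rates by grade are 23.0, 13.0 and 7.0% on placebo and 43.0, 27.4 and 15.9% on active.

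- Within-grade variance: 0.35 x (0.2451 + 0.1771) + 0.40 x (0.1989 + 0.1131) + 0.25 x (0.1337 + 0.0651) = 0.3223.
- Half the variance of the risk difference across grades: 0.5 x (0.0243 - 0.15^2) = 0.0009.
- Adjusted variance term 0.3232; reduction 1 - 0.3232/0.3375 = 4.2%, or about 10 of 236 subjects.
- Power: 2.805 / sqrt(1 - 0.042) - 1.960 = 0.906, giving 81.7%.

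The same steps give a reduction of 1.6% at OR 1.5 (power 80.7%) and 9.4% at OR 3 (power 83.8%, about 22 subjects).

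**3. Simulation of the actual tests.** N = 236, 15% vs 30%, grade mix 35/40/25%, 20,000 trials per case. The planned CMH is compared with a logistic score test that includes age group, pre-dose severity and the grade as one linear term.

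| OR per grade | Planned CMH | Score test, unscaled | Gain after scaling |
|---|---|---|---|
| 1 | 79.5% | 79.9% | 0.0 |
| 1.5 | 80.1% | 81.2% | 0.7 |
| 2 | 80.0% | 82.3% | 1.9 |
| 3 | 79.6% | 83.8% | 3.7 |

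The paired standard error is 0.10 to 0.19 points. The unscaled score test is slightly liberal: type I error 0.051 to 0.054, against 0.050 to 0.052 for the CMH. The last column multiplies the score chi-square by (N - 4)/N = 232/236 = 0.983, which brings type I error to 0.049 to 0.052.

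Two further simulations agree. Calibrating critical values under a common null (25,000 runs per case) gave gains of about 0.1, 0.7, 1.6 and 3.9 points. Another run with the (N - 4)/N scaling gave about 0, 0.3 to 0.6, 1.2 to 1.7 and 3 to 4; there the gain remained when the grade was correlated with Attack 2 pre-dose severity.

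**4. Extra CMH strata instead.** Crossing the three grades with the existing strata makes 12 cells of about 20 subjects. In a 20,000-run simulation with the same grade mix, power went from 79.4% to 77.8% at OR 1, from 79.0% to 79.3% at OR 2, and from 79.2% to 81.8% at OR 3. This route costs power when the grade is uninformative and only breaks even near OR 2.

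**The case against.** The strongest reply is that nothing is wrong with the plan. The CMH includes the randomization factor and pre-dose severity, controls its error rate and delivers the power claimed, so choosing another valid covariate set is a preference. This stands. A reader might infer that the planned test is deficient or the trial underpowered by its own assumptions; step 1 shows that it is neither.

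Second, the gain is conditional. A reader might infer that the trial certainly gives up precision, but no section gives the prognostic strength. One crude anchor points low. Suppose the adult placebo rate of 17.3% were the unselected rate and the assumed 15% were the rate after removing Attack 1 responders. Responders would then have an Attack 2 rate of (0.173 - 0.827 x 0.15)/0.173 = 28.3%. The correlation between attacks is (0.283 - 0.173)/0.827 = 0.13, R2 is about 1.8%, and the saving is about 4 subjects. The anchor is weak: it sets an observed adult rate against an assumed adolescent one, and it concerns yes/no response, not the grade among non-responders. It is still a fair warning that the gain may be small.

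Third, it is tempting to say that the grade exists for everyone. Inclusion criterion 8 requires only 75% diary entry for Attack 1, so a 120-minute grade can be missing. The severity row of Table 2 is also broken in the text version. Collection at 120 minutes is inferred from 6.1.2 and from the endpoint of relief at 120 minutes, and should be confirmed.

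Fourth, adjustment does not lower a high placebo response rate; only the run-in exclusion aims at that. This stands. The case for adjusting is precision alone.

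The objection that pre-dose severity already captures the grade's information does not remove the gain: it persisted when the two were correlated.

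**Conclusion.** The point holds as an efficiency improvement, not as an error. The plan leaves a legitimate baseline covariate out of a primary test that has about 80% power and no margin. After correcting for test size, the gain is roughly 0 points at an odds ratio of 1 per grade, 0.5 at 1.5, 1.5 to 2 at 2, and 3 to 4 at 3, with no measurable loss when the grade is uninformative. The small apparent gain of the unscaled score test at an odds ratio of 1 comes from its slightly liberal size, not from precision.

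From a base of 80% power, the factor ((1.960 + z_new)/(1.960 + 0.842))^2 turns 1.5 to 2 points into about 9 to 13 subjects out of 236, and 3 to 4 points into about 19 to 26.

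These figures rest on assumed grade distributions and odds ratios, a roughly linear effect of grade on the logit scale, and few missing grades.

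**What to change.** Before unblinding, amend 8.2 and the synopsis as follows.

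- **Primary test:** the score test for treatment from a logistic model with age group, Attack 2 pre-dose severity and the Attack 1 120-minute grade (1, 2, 3) as one linear term, with a small-sample scaling such as (N - 4)/N on the chi-square.
- **Estimate:** a standardized risk difference with its confidence interval.
- **Missing grades:** a stated rule, for example a missing indicator.
- **Supportive test:** the planned age by severity CMH.
- **Not recommended:** adding the grade as further CMH strata.

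If the sponsor keeps the CMH as primary, the adjusted model can be pre-specified as the first supportive analysis, but that recovers none of the power of the primary test.

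The cost is wording in two places and a few lines of code. No new data or patients are needed. The downside is that the primary test becomes model-based and depends on a missing-grade rule.
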